11.3. Description of Subgroups to be Analyzed

Descriptive analyses will be performed for the primary efficacy endpoint for the following subgroups using the FAS with details provided in the Statistical Analysis Plan (SAP):

- Subject Demographics
 - Gender
 - Race/Ethnicity
 - Age (categories: 18-30, 31-40, 41-60, > 61yrs.)
- Baseline Disease Characteristics
 - Duration of Meniere's Disease
 - Previous intratympanic steroid injection for Meniere's Disease
 - Degree of hearing loss

11.4. Subject Demographics, Baseline Disease Status, and Disposition

Descriptive statistics for subject demographics, baseline disease status, and subject disposition will be provided.

11.5. Efficacy Evaluations

11.5.1. Primary Efficacy Endpoint

The primary efficacy endpoint is the number of definitive vertigo days (DVD) at Week 12 (the 4-week (28-day) interval from Week 9 through Week 12). A DVD is defined as each day the subject recorded a vertigo episode lasting at least 20 minutes and corresponds to a Vertigo Score of 2 or more. If multiple episodes occur on a given day, only the worst episode in terms of score should be recorded.

11.5.2. Secondary Efficacy Endpoints

Secondary Efficacy Endpoint:

- The number of definitive vertigo days (DVD) at Week 8 [the 4-week (28-day) interval from Week 5 through Week 8]
- The number of definitive vertigo days (DVD) at Week 4 [the 4-week (28-day) interval from Week 1 through Week 4]
- The change from baseline in vertigo frequency (VF) during the 4-week study interval (Week 9 through Week 12), where vertigo frequency is defined as the proportion of days during the 4-week interval where a definitive vertigo episode was recorded divided by the number of non-missing diary entries for the relevant interval
- The change from baseline with respect to severity of vertigo episodes as measured by the mean Vertigo Score during the 4-week study interval (Week 9 through Week 12)
- The change from baseline in average daily count of vertigo episodes, during the 4-week study interval (Week 9 through Week 12)
- Occurrence of Normal activity, Slight limitation, Moderate limitation, Sick at home, and Bed ridden events as a consequence of vertigo at Week 12
- SF-36 at Week 12
 - Physical Health Summary Measure
 - Mental Health Summary Measure
 - o 8 Scales

11.5.3. Exploratory Efficacy Endpoints

Exploratory Efficacy Endpoints are:

• The change from baseline in vertigo frequency (VF) during each 4-week study interval (Week 1 through Week 4) and (Week 5 through Week 8), where vertigo frequency is defined as the proportion of days during the 4-week interval where a definitive vertigo episode was recorded divided by the number of non-missing diary entries for the relevant interval

- The change from baseline with respect to severity of vertigo episodes as measured by the mean Vertigo Score during each 4-week study interval (Week 1 through Week 4) and (Week 5 through 8)
- The change from baseline in average daily count of vertigo episodes, during each 4-week study interval (Week 1 through Week 4) and (Week 5 through Week 8)
- Occurrence of Normal activity, Slight limitation, Moderate limitation, Sick at home, and Bed ridden events as a consequence of vertigo at Week 4 and Week 8
- SF-36 at Weeks 4 and 8
 - Physical Health Summary Measure
 - Mental Health Summary Measure
 - o 8 Scales
- Tinnitus Functional Index (TFI) at Weeks 4, 8, and 12

Details regarding imputation of missing data, including items for questionnaires, will be provided in the Statistical Analysis Plan (SAP).

11.5.4. Analytic Methods for Efficacy

The primary efficacy endpoint is the number of DVD at Week 12 (the 4-week (28-day) interval from Week 9 through Week 12). Poisson regression model will be used to estimate and compare the mean number of DVD for OTO-104 and placebo groups during the primary endpoint 4-week study interval. The model will include treatment group (OTO-104 vs. placebo) and gender as factors (categorical), and the lead-in period as a covariate. An offset for the number of diary entries recorded for that 4-week interval (interval from Week 9 through 12) will be included for each subject. The number of lead-in period DVD will be adjusted to 28 days. The model will also adjust for over-dispersion using Pearson residuals as the scale factor.

The primary analysis population for the comparison of the primary endpoint between the treatment groups in this study is full analysis set (FAS). Subjects will be included in the treatment group to which they were randomized regardless of the actual study drug received.

The primary endpoint analysis also will be conducted using per-protocol, ITT, and completers analysis sets as sensitivity analyses.

If a subject has no recorded diary data for the Vertigo Severity Score during Week 12 interval then an imputation method which will be specified in the SAP will be used.

The secondary efficacy endpoints of number of DVD during 4-week study interval (Week 1 through Week 4) and (Week 5 through Week 8) will be compared between the treatment groups separately using the same Poisson regression model specified for the primary endpoint.

The secondary efficacy endpoint of change from baseline in vertigo frequency (VF) at Week 12 (the 4-week interval from Week 9 through Week 12), will be compared between the treatment groups using analysis of covariance (ANCOVA). The model will contain treatment group (OTO-104 vs. placebo) and gender as factors (categorical) and baseline vertigo frequency as a covariate.

The secondary efficacy endpoint of change from baseline in severity of vertigo during 4-week study interval (Week 9 through Week 12) will be compared between the treatment groups using ANCOVA including treatment groups, gender, and severity score at baseline as a covariate.

The secondary efficacy endpoint of change from baseline in average daily count of vertigo episodes, during 4-week study interval (Week 9 through Week 12) will be compared between the treatment groups using ANCOVA including treatment groups, gender, and average daily count of vertigo episode at baseline as a covariate.

The secondary endpoint of occurrence of Normal activity, Slight limitation, Moderate limitation, Sick at home, and Bed ridden events as a consequence of vertigo at Week 12 will be compared between the treatment groups using Mantel-Haenszel Row Mean Scores stratified by gender.

Alternative models will be pre-specified in the SAP should certain assumptions regarding data and models do not hold. In addition, the SAP will include pre-specified data transformations should evaluation of the residuals suggest a data transformation is more suitable.

If the primary endpoint comparison between the two treatment groups is statistically significant in favor of OTO-104 then a closed testing, gate-keeping procedure will be used to compare the following secondary efficacy endpoints sequentially:

- 1. The number of DVD at Week 8 [the 4-week (28-day) interval from Week 5 through Week 8]
- 2. The number of DVD at Week 4 [the 4-week (28-day) interval from Week 1 through Week 4]

In this procedure if the first secondary endpoint comparison between the two treatment groups is statistically significant in favor of OTO-104 then the second secondary endpoint will be compared and tested. If the comparison of the first secondary endpoint is not statistically significant in favor of OTO-104 then the reported p-value for the second secondary endpoint will be considered as a nominal p-value.

The remaining secondary endpoints comparison will not follow the gate keeping procedure and therefore the reported p-values will be reported as nominal p-values. This procedure controls the study-wise Type I error. Since the study-wise error is maintained with the above procedure, there is no α penalty associated with it. All efficacy hypothesis tests will be 2-sided and performed at $\alpha = 0.05$ significance level.

11.6. Safety Evaluations

Safety endpoints to be examined include:

- Vital Signs, Height and Weight Measurements
- Clinical Laboratory Test
- Tympanometry
- Audiometry
- Otoscopy
- C-SSRS Assessment

- Concomitant Medications
- Adverse events

Descriptive statistical tabulations will be presented for all subjects included in the Safety Analysis Set.

11.6.1. Adverse Events

The current version of Medical Dictionary for Regulatory Activities (MedDRA), as indicated in the Data Management Plan, will be used to code all AEs.

The primary analysis of AEs will consider only treatment-emergent AEs, events occurring for the first time, or worsening during or after the first dose of study drug. Subject incidence of TEAEs and SAEs will be tabulated by preferred terms and system organ class. Severity and relationship to study drug will also be presented. For summary tables, a subject who experiences the same coded event more than once is counted only one time for that coded event at the highest severity level. AEs will be presented by descending order of frequency in MedDRA system organ class and preferred term.

Subgroup analyses for age, race, and gender will also be examined provided a reasonable number of subjects in each subgroup are available for analysis. Listings of all SAEs, AEs leading to study withdrawal, and deaths on-study will also be included. Duration and outcome of each AE will be reported in subject listings.

Adverse events occurring during the lead-in period prior to exposure to study drug will be reported in data listings. Further details will be provided in the SAP.

11.6.2. Vital Signs and Laboratory Parameters

The analysis of vital signs and laboratory parameters will include descriptive statistics for the change from baseline to the endpoint visit, change from baseline for each visit (vital signs only). Where appropriate, analyses will also include shifts from baseline to the endpoint visit. For laboratory values, the normal ranges will be used to determine the classifications. Values below the normal range will be classified as low, values above the normal range will be classified as high, and values within the normal range will be classified as normal.

11.6.3. Otoscopic Examinations

Observations recorded during the conduct of otoscopic exams will be descriptive in nature. The number and percent of subjects presenting with each Otoscopic classification will be provided by treatment group and study visit. Where relevant, the number and proportion of subjects with changes in their otoscopic classification from baseline to the endpoint visit will also be provided for each treatment group.

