	Screening	Lead-In	Baseline ¹ / Treatment Visit	Follow-up Visit	Follow-up Visit	End-of-Study/ Early Termination	Unscheduled Visit
	Visit 1	_	Visit 2	Visit 3	Visit 4	Visit 5 ²	Unscheduled
	_	-	-	Week 4	Week 8	Week 12	N/A
Procedure	Up to 14 days prior to start of lead-in	Day -28 to -1 (+3 days)	Day 1	Day 28 (±2 days)	Day 56 (±2 days)	Day 84 (+4 days)	N/A
Administer study drug			X				
Adverse event monitoring			X	X	X	X	X

¹ Baseline assessments on Day 1 are to be performed before administration of study drug shown. Review eligibility criteria at the baseline visit to ensure subjects remain eligible following the lead-in period.

² Procedures scheduled for Visit 5 will be performed at the end of the follow-up period (+4 days) or upon early discontinuation from the study.

³ Once the subject has met the inclusion/exclusion criteria as appropriate at screening, the subject will enter a 4-week lead-in period. During the lead-in, the subject will record their daily vertigo experience. A determination of whether the subject meets Inclusion Criteria No. 10 and 11 will be determined 28 days after subjects enter the lead-in period.

⁴ Medical history to include information on demographics.

⁵ Vital sign measurements include blood pressure and pulse rate.

⁶ Only weight is to be measured at Visit 5.

⁷ Female subjects of childbearing potential will have a serum pregnancy test at screening and a urine pregnancy test at baseline, prior to randomization. If the screening or baseline pregnancy test result is positive, the subject is not eligible for enrollment into the study. If a subject is found to be pregnant after dosing with study drug, they will complete the follow-up period. All serum pregnancy tests will be analyzed by a central laboratory. Serum pregnancy test results from Visit 1 as well as the urine pregnancy test at baseline prior to randomization must be included in eligibility assessment at Visit 2.

⁸ Clinical laboratory tests include hematology, clinical chemistry, and urinalysis and will be analyzed by a central laboratory.

⁹ Columbia-Suicide Severity Rating Scale: The Baseline version will be used at the Screening visit and the Since Last Visit version will be used at all subsequent visits.

¹⁰Subjects will be instructed and trained how to record daily vertigo experience using the IVRS diary.

[figure not shown]

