8.3.5. Otoscopy

Otoscopic exams will be used to assess the auditory canal, the appearance of the tympanic membrane, and the healing of the intratympanic injection site. Otoscopic examinations will be performed in both ears at all study visits during the study by the physician. Presence and size of tympanic membrane perforations will be recorded. Perforations of the tympanic membrane will be captured as AEs only if the perforation increases in size and does not resolve by the end of the study. Subjects wearing hearing aids should be instructed not to wear their hearing aids during the otoscopic exam.

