8.3.6. C-SSRS Assessment

The C-SSRS assessment will be administered at all study visits. The Baseline version will be used at Visit 1 for all subjects. For Visits 2 through 5, the Since Last Visit version will be used. Any subject with a positive score at on the Baseline version or an appearance of any new suicidal ideation or suicide behavior since the Baseline version should be referred to their primary care provider for follow-up.

If a subject has any post-Screening C-SSRS score of 1-3 for Ideation (i.e., a "yes" answer to Questions 1, 2, or 3) or a "yes" response to the Non-Suicidal Self-Injurious Behavior question) and the score is higher than the Screening C-SSRS score, then this assessment should be recorded as an AE. This information is reported as indicated in Section 9. (Possible AE terms: Suicidal plans, Suicidal ideation, Suicidal tendency, Suicidal behavior, Suicidal intention, Suicidal depression, Active suicidal ideation, Passive suicidal ideation, Self-injurious behavior without suicidal intent).

If a subject has any post-Screening C-SSRS score of 4 or 5 for Ideation (i.e., a "yes" answer to question 4 or 5) and/or any questions answered yes for Suicidal Behavior (with the exception of a "yes" response to the Non-Suicidal Self-Injurious Behavior question), and this was not observed at Screening, then this assessment should be recorded as a Serious Adverse Event (SAE). This information is reported as indicated in Section 9.2.2.

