11.6.6.2. Since Last Visit Version

The Since Last Visit version of the C-SSRS will be administered at each study visit after the Screening visit (Visit 1). The same overall individual variables for suicidal ideation and behavior will be assessed as in the Baseline version. In addition, overall suicidality (yes/no) will be defined as any subject having any suicidal ideation or behavior since the last visit. All suicidal ideation and behavior variables will be tabulated overall and by treatment group for each study visit. All C-SSRS data will be included in data listings.

Any subject with an appearance of any new suicidal ideation or suicide behavior since Screening should be referred to their primary care provider for follow-up.

If a subject has any post-Screening C-SSRS score of 1-3 for Ideation (i.e., a "yes" answer to Questions 1, 2, or 3) or a "yes" response to the Non-Suicidal Self-Injurious Behavior question) and the score is higher than the Screening C-SSRS score, then this assessment should be

recorded as an AE. This information is reported as indicated in Section 9.2.1. (Possible AE terms: Suicidal plans, Suicidal ideation, Suicidal tendency, Suicidal behavior, Suicidal intention, Suicidal depression, Active suicidal ideation, Passive suicidal ideation, Self-injurious behavior without suicidal intent).

If a subject has any post-Screening C-SSRS score of 4 or 5 for Ideation (i.e., a "yes" answer to question 4 or 5) and/or any questions answered yes for Suicidal Behavior (with the exception of a "yes" response to the Non-Suicidal Self-Injurious Behavior question), and this was not observed at Screening, then this assessment should be recorded as a Serious Adverse Event. This information is reported as indicated in Section 9.2.2.

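### No specified table counts the subjects per arm with any post-injection tympanic membrane perforation, and unscheduled otoscopy has no stated place in the tables

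*Combined protocol and SAP*

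**What the plan says.** **Otoscopy tables.** Section 11.6.3 specifies two displays. The first is by visit: "The number and percent of subjects presenting with each Otoscopic classification will be provided by treatment group and study visit". The second covers, where relevant, subjects with "changes in their otoscopic classification from baseline to the endpoint visit will also be provided for each treatment group".

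**Perforations and adverse events.** Section 8.3.5 has presence and size recorded at otoscopy. It then says that perforations are "captured as AEs only if the perforation increases in size and does not resolve by the end of the study"; the opening text of Section 9 repeats the rule.

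**Unscheduled visits.** Table 1 marks otoscopy and the C-SSRS with an unqualified X in the unscheduled column. Tympanometry, audiometry and laboratory tests are marked there only as indicated. Section 11.6.3 does not mention unscheduled examinations.

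**C-SSRS.** After Screening, "the Since Last Visit version will be used at all subsequent visits" (Table 1, footnote 9). Section 11.6.6.2 states: "All suicidal ideation and behavior variables will be tabulated overall and by treatment group for each study visit". Its summary variable also works visit by visit: "overall suicidality (yes/no) will be defined as any subject having any suicidal ideation or behavior since the last visit". Section 11.6.6.2 further provides that "All C-SSRS data will be included in data listings".

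**The concern.** The drug is injected through the tympanic membrane, otoscopy is the protocol's named measure of local tolerability, and the secondary objective is to describe safety. A reader will want to know how many subjects in each arm had a perforation after the injection. By-visit percentages are prevalences at Weeks 4, 8 and 12 and do not add up to that number. The baseline-to-endpoint change leaves out any perforation that has closed by Week 12. The adverse event tables in 11.6.1 do count each subject once, but most perforations never reach them.

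The first scheduled post-dose otoscopy is at Day 28 (±2 days). A perforation found at an unscheduled visit before then, and closed by Day 28, is the case most easily lost. An unscheduled visit may well be made because of a problem, so its findings should have a defined place in the tables.

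**Working it through.** **1. Can any specified table supply the count?** The plan states no perforation rate or ever-affected figure, so there is nothing to reproduce. The displays compare as follows:

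- By-visit table (11.6.3): gives prevalence at each visit. A subject seen at two visits is in two rows, and overlap cannot be read from the margins.
- Baseline-to-endpoint change (11.6.3): misses every perforation that has closed by the endpoint visit.
- Adverse event incidence (11.6.1): counts once per subject, but a perforation enters only if it both enlarges and remains unresolved (8.3.5, Section 9). One that persists without enlarging, or enlarges and then heals, is absent.

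None of the three gives subjects with any post-injection perforation.

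**2. Where do unscheduled examinations go?** Section 8.3.3 has tympanometry at all study visits, yet Table 1 requires it at unscheduled visits only as indicated. This suggests that the phrase means Visits 1 to 5. Section 8.3.5 uses the same phrase for otoscopy, and there Table 1 has an unqualified X. This fits a meaning that includes unscheduled visits. The text does not settle the matter.

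**3. How far can by-visit rows fall short?** Inputs: 3 scheduled post-dose visits (Section 3, Table 1) and 80 subjects per arm (Section 11.1). The rate is an assumption: 4 of 80 (5%) at each visit. If m is the largest by-visit count, the number ever affected lies between m and the sum of the three counts, which is at most 3m.

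- Same subjects throughout: 4/80 = 5%, ratio 1.0.
- No overlap: 12/80 = 15%, ratio 3.0.
- Independent visits: 1 − (1 − 0.05)³ = 14.3%, ratio 2.85. At 2%, 10% and 20% per visit the ratio is 2.94, 2.71 and 2.44.
- Visit-to-visit persistence r at constant prevalence p: share = 1 − (1 − p)(1 − q)², with q = p(1 − r)/(1 − p). At p = 5%, r = 50%, 75% and 90% give 9.9%, 7.5% and 6.0%, with ratios 1.99, 1.50 and 1.20.
- Declining counts of 4, 2 and 1: between 4 and 7 subjects, ratio 1.0 to 1.75.

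For a perforation made on Day 1 that does not reopen, anyone affected at Week 8 or 12 was also affected at Week 4. If all visits are attended, the scheduled-visit total then equals the Week 4 count and the ratio is 1.

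**4. Findings seen only at unscheduled visits.** If these are left out of the tables, they come on top. With 1, 2 or 4 such subjects, the no-overlap extreme becomes 13/4 = 3.25, 14/4 = 3.5 or 16/4 = 4.0. If the visit rows are all zero, the tables show 0 where the true share is 1.25%, 2.5% or 5% of 80.

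**5. Does the same gap exist for suicidality?** Mostly not. Under 8.3.6, ideation of 1 to 3, or non-suicidal self-injury, becomes an adverse event when it is present after Screening "and the score is higher than the Screening C-SSRS score, then this assessment should be recorded as an AE". Ideation of 4 or 5, or suicidal behavior, not seen at Screening becomes a serious adverse event. Section 11.6.1 counts each once per subject per coded event. Two gaps remain. The Screening comparator is lifetime history (11.6.6.1), so a recurrence not above it is not an adverse event. Section 8.3.6 also offers nine possible terms, so the count may be split across preferred terms.

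**The case against.** The strongest reply is that by-visit percentages are correctly labelled prevalences that make no claim to be cumulative. The objective is descriptive, the data are recorded, and Section 11 defers detail to an SAP to be finalised before unblinding. All of this stands. The text available for review contains no separate SAP, so the gap is shown for Section 11 of the protocol only. It also means that the trial could produce the count from collected data; the point is that no specified table does so.

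Three stronger readings are tempting, and the documents do not support them:

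- **That incidence is understated threefold.** Three is the no-overlap extreme for scheduled visits. It would need different subjects to be newly positive at each of Weeks 4, 8 and 12 after one injection on Day 1. Nor is it a ceiling once findings seen only at unscheduled visits are considered.
- **That suicidality is missed or cannot be stated.** New or worsened results become adverse events or serious adverse events, and all C-SSRS data are listed. Visit 2 is pre-dose, but a by-visit table shows it separately, so it does not contaminate the post-dose rows.
- **That unscheduled examinations are excluded.** Section 11.6.3 is silent on them. Silence is a reason to specify their handling and does not show that they will be omitted.

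No parallel change to tympanometry is warranted: 11.6.5 already gives shifts to each post-baseline visit.

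**Conclusion.** The point holds for otoscopy. As written, no specified table gives the number of subjects per arm with any post-injection perforation, and the adverse event rule prevents the adverse event tables from doing so. A perforation seen only at an unscheduled visit and closed by the next scheduled one could be in no by-arm table.

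The size is unknown, because the plan gives no rate. For scheduled visits the ever-affected share is 1 to 3 times the largest by-visit share. For perforations from the single Day 1 injection it is probably near 1, assuming that they do not reopen and that visits are attended. Findings made only at unscheduled visits would be additional if the tables omit them, and this part cannot be bounded from the documents.

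For the C-SSRS only a minor gap remains: recurrences not above the lifetime Screening score, and the lack of a single count across preferred terms.

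**What to change.** Keep the by-visit tables and add to 11.6.3, before unblinding: *The number and percent of subjects with a tympanic membrane perforation (and each other abnormal otoscopic finding) in the treated ear at any post-dose assessment, scheduled or unscheduled, will be tabulated by treatment group, each subject counted once at the worst result.*

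As a minor parallel, add to 11.6.6.2 one any-post-dose row for ideation and one for behavior, covering scheduled and unscheduled visits and leaving out the pre-dose Visit 2 responses.

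The cost is SAP wording and one extra table per assessment, from data already collected, with no change to study procedures. The reported perforation rate may be slightly less favourable than the by-visit rows suggest.
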